## **2 Protocol-designed statistical methods and sample size determination (Section 9.7 of Clinical Study Report)**

### **2.1 Statistical and analytical plan**

Statistical analysis of this clinical study will be performed according to "Statistical Principles for Clinical Trials" (Evaluation and Licensing Division, PMSB 1047 dated November 30, 1998).

#### **2.1.1 Analysis set**

The analysis sets are defined as follows. In addition, if judgement of inclusion/exclusion of a patient such as a deviated patient is difficult, inclusion/exclusion of the case in the analysis set will be determined at the Case Review Committee.

##### **2.1.1.1 Safety population**

All the patients who received the assigned study drug will be included in the Safety Population (SP).

##### **2.1.1.2 Efficacy analysis set**

Of any assigned patients, any patients excluding those who did not receive the study drug or those from whom no information on efficacy was available after allocation are defined as the Full Analysis Set (FAS). In this study, an analysis will be performed in the FAS. In addition, any patients in the FAS excluding those with major protocol violations after start of treatment and for whom the efficacy is evaluable are defined as the Per Protocol Set (PPS). Analysis of the primary endpoint will be performed in the PPS.

##### **2.1.1.3 Randomized patients**

Patients assigned with an allocation code are regarded as Randomized Patients.

#### **2.1.2 Analysis item and analytical method**

##### **2.1.2.1 Breakdown of patients**

(1) Analysis set : Randomized Patients

(2) Analytical method :

- 1) The number of patients who were treated, completed, or discontinued and the proportion will be summarized by treatment group (number of patients, %).
- 2) The number of discontinued patients and the proportion in each reason for discontinuation will be summarized by treatment group (number of patients, %).
- 3) A list of discontinued patients will be prepared.

##### **2.1.2.2 Breakdown of analysis set**

(1) Analysis set : Randomized Patients

(2) Analytical method :

- 1) The number of patients who were included in or excluded from each analysis set and the proportion will be summarized by treatment group (number of patients, %).
- 2) A list of the patients who were excluded from the analysis set will be prepared.

**2.1.2.3 Background factors of the patients**

(1) Analysis set : SP, FAS

(2) Analysis item :

< Continuous variable >

Age, height, body weight, BMI, oxygen-saturation (SpO2) at screening

< Categorical variables >

Sex, age (<40, 40≤ to <65, 65≤ to 75<, 75≤), BMI(<30, 30≤), oxygen saturation (SpO2) at screening (<90%, >90%), history of alcohol intake, smoking history, with or without concomitant use of antiviral drugs for COVID-19, with or without concomitant use of steroids and their classes (dexamethasone, methylprednisolone or prednisolone, others[mixture of dexamethasone and methylprednisolone or prednisolone]), with or without concomitant use of JAK (Janus kinase) inhibitors, category on a 7-point ordinal scale at baseline, presence or absence of comorbidity (heart disease [myocardial infarction, congestive heart failure], cerebrovascular disease, dyslipidemia, hypertension, diabetes, and bronchial asthma), time since onset (<10 days, 10 days≤)

(3) time point : at screening, Day 0

(4) Analytical method

BMI will be derived.

<BMI>BMI is calculated using height and body weight.

Height at the screening will be used for calculation of BMI.

$$\bullet \text{BMI} = \text{Body weight(kg)} / \text{Height(m)}^2$$

- 1) Continuous variables : Summary statistics (number of patients, arithmetic mean, standard deviation, median, minimum, maximum) will be calculated by treatment group. In addition, the p-value (two-sample t-test) will be calculated.
- 2) Categorical variables : The number of patients and the proportion will be summarized by treatment group (number of patients, %). In addition, the p-value (chi-square test) will be calculated.

**2.1.2.4 Medical history/current medical condition**

(1) Analysis set : SP

(2) Analysis item: medical history, current medical condition

(3) Time point : at screening

(4) Analytical method

Diagnostic names described in the Case Report Form will be read using the specified version of the MedDRA.

- 1) The number of patients and the proportion will be summarized by SOC and PT in each treatment group (number of patients, %).
- 2) A list of medical history and current medical conditions of the patients will be prepared. Analysis set : Randomized Patients

#### **2.1.2.5 Concomitant medication**

- (1) Analysis set : SP
- (2) Analysis item : concomitant drug
- (3) Time point : at screening to Day 14
- (4) Analytical method :

The drug name described in the Case Report Form will be changed to the generic name using WHO-DD.

- 1) The number of patients who are taking concomitant drugs and the proportion will be summarized by drug name (generic name) in each treatment group (number of patients, %).
- 2) A list of concomitant drugs taken by the patients will be prepared. Analysis set : Randomized Patients

#### **2.1.2.6 Standard medication**

- (1) Analysis set : SP
- (2) Analysis item : standard drug
- (3) Time point : at screening to Day 14
- (4) Analytical method :

The drug name described in the Case Report Form will be changed to the generic name using WHO-DD.

- 1) The number of patients who are taking standard drugs and the proportion will be summarized by drug name (generic name) in each treatment group (number of patients, %).
- 2) A list of standard drugs taken by the patients will be prepared. Analysis set : Randomized Patients

#### **2.1.2.7 Concomitant therapy**

- (1) Analysis set : SP
- (2) Analysis item : combination therapy
- (3) Time point : at screening to Day 14
- (4) Analytical method :

- 1) The number of patients who are receiving concomitant therapies and the proportion will be summarized by therapy in each treatment group (number of patients, %).
- 2) A list of concomitant therapies received by the patients will be prepared. Analysis set : Randomized Patients

#### **2.1.2.8 Standard therapy**

- (1) Analysis set : SP
- (2) Analysis item : standard therapy
- (3) Time point : at screening to Day 14
- (4) Analytical method :

- 1) The number of patients who are receiving standard therapies and the proportion will be summarized by therapy in each treatment group (number of patients, %).
- 2) A list of standard therapies received by the patients will be prepared. Analysis set : Randomized Patients

### 2.1.2.9 Treatment compliance of study drug

- (1) Analysis set : SP, FAS
- (2) Analysis item : number of doses
- (3) Time point : Day 1 to Day 10
- (4) Analytical method :
  - 1) Summary statistics (number of patients, arithmetic mean, standard deviation, median, minimum, and maximum) for the number of doses will be calculated by treatment group. In addition, the number of patients and the proportion will be summarized by the number of doses in each treatment group (number of patients, %).
  - 2) The number of patients and the proportion will be summarized by the reasons for discontinuation in each treatment group (N, %).
  - 3) A list of the treatment compliance and the reasons for discontinuation of the study drug will be prepared. Analysis set : Randomized Patients

### 2.1.2.10 Efficacy Evaluation

#### 2.1.2.10.1 Primary endpoint

- (1) Analysis set : FAS, PPS
- (2) Analysis item : period to the first improvement by at least 2-rank between baseline and Day 28 on a 7-point ordinal scale.
- (3) Time point : Day 0 to Day 28
- (4) Analytical method : The following analysis will be performed.
  - 1) As the main analysis, the improvement rate will be estimated by treatment group using Kaplan-Meier method, and the comparison between groups using the log-rank test with a significance level of 5% will be performed as well. In addition, assessment using Cox's proportional hazards model with the presence or absence of concomitant antiviral drugs for COVID-19 as a covariate will be performed. Definitions of the events and censoring are presented in Table 2.3.

Table 2.1 7-Point ordinal scale

Category	ordinal scale
1	Have died
2	Use an invasive ventilator or ECMO
3	Use a noninvasive ventilator or high-flow oxygen supply device
4	Require oxygen supply
5	Do not require oxygen supply but require continuous therapy (related to COVID-19 or others)
6	Do not require both oxygen supply and continuous therapy
7	Have been discharged from hospital

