- (2) As an evaluation of the drug for COVID-19 from clinical standpoint, "number of days until discharge from hospital" considered to be equally important with "number of days to achieve at least 2-rank improvement on a 7-point ordinal scale" was set.
- (3) In order to visualize the inhibitory effects of sargramostim on the shifting of disease condition to more severe condition from a simple pneumonic condition, proportion of subjects whose category

has shifted to Category 1 or 2 (worsening to use of invasive ventilator or worse) on a 7-point ordinal scale until Day 28 was set as an index.

- (4) This endpoint was set in order to evaluate the effect of sargramostim on pneumonia.
- (5) This endpoint was set in order to evaluate the effect of sargramostim on pulmonary function.
- (6) This endpoint was set in order to evaluate the effect of sargramostim on the inflammatory changes.
- (7) Data derived from the same measurement parameter as those for the primary endpoint were to be assessed secondarily from different point of view. In addition, since the disease condition requiring treatment may likely be persistent in a COVID-19 patient requiring hospitalization, the assessment time was set not only on Day 14 but also on Day 28.
- (8) Oxygen supply is considered to be one of the clinical indicators to assess respiratory failure and thus was set as a categorized ordinal scale.
- (9) Since the data on inhalation administration of sargramostim to Japanese population as well as the data on the pathology of COVID-19 over time in Japanese population will be valuable, an exploratory endpoint will be added as needed.

5.2.1.1 Number of days to achieve at least 2-rank improvement on a 7-point ordinal scale

The clinical condition of a subject will be comprehensively measured at the timing specified in "2 Observation and Examination Schedule" and will be evaluated according to "13.3 7-point ordinal scale" by the investigators.

Assessment on Day 0 will be used as a baseline value, and the number days to achieve at least 2-rank improvement (see Table 13.3-1) from baseline will be assessed.

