Considering the mechanism of action of sargramostim, patients with clinically diagnosed pneumonia whose respiratory function is suggestively decreased are to be included in the study. In addition, patient population without use of invasive ventilator yet (the category of a patient that falls into one of Category 3 to 5 on a 7-point ordinal scale (see Table 13.3-1)) is to be chosen in order that an accurate dose of study drug can be administered by inhalation.

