#### 2.1.2.10.2.10 Other items specified as exploratory

- (1) Regarding "No longer required ongoing medical care" defined in Category 6 on the 7-point ordinal scale, period to improvement by at least 2-rank on a 7-point ordinal scale will be recalculated in the case that the end of treatment during tapering of steroid therapy according to the patient's condition has been defined. And similar analysis to the primary endpoint will be performed. The analysis will be performed only in the FAS. The end of treatment is defined as "use of dexamethasone 4 mg (equivalent to prednisolone 25 mg or methylprednisolone 20 mg) or less."
- (2) Similar analysis to that in Section 2.1.2.10.2.2 will be performed for the period from baseline to shifting to Category 5 on a 7-point ordinal scale. Patients who are in Category 3 or 4 at baseline on a 7-point ordinal scale will be included in the analysis. Definitions of event/censoring are presented in Table 2.3.
- (3) Similar analysis to that in Section 2.1.2.10.2.2 will be performed for the period from baseline to improvement by at least 1 rank on a 7-point ordinal scale. Definitions of events/censoring are presented in Table 2.3.

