#### 2.1.2.15 Subgroup analysis

A subgroup analysis for the analysis defined in Section “2.1.2.10.1 primary endpoint” will be performed (only in the FAS). The factors for subgroup are as follows.

- Sex
- Age (<65 years,  $\geq 65$  years)
- With or without concomitant use of antiviral drugs for COVID-19 (excluding Cox's proportional hazards model)
- Class of steroid used (dexamethasone, methylprednisolone or prednisolone, other [mixture of dexamethasone and methylprednisolone or prednisolone])
- Baseline category on a 7-point ordinal scale (3/4/5)

A subgroup analysis for the analysis defined in 2) of Section “2.1.2.11.1.1 AE and ADR” will be performed. The factors for subgroup are as follows.

- Sex
- Age (<65 years,  $\geq 65$  years)
- With or without concomitant use of antivirals drugs for COVID-19

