#### 4.7 SAS Code

- SAS Code for implementing Cox regression model is shown below.

```
ods output ParameterEstimates = [OUTPUT];
proc phreg data = [DATASET];
  class [GROUP] [THERAPY];
  model [TARGET] * [CENSOR FLG](0) = [GROUP] [THERAPY] / rl alpha = 0.05;
run;
```

- SAS Code for implementing MMRM model is shown below.

```
proc mixed data = [DATASET];
  class [SUBJECT] [VISIT] [GROUP];
  model CHG = BASE [VISIT] [GROUP] [VISIT] * [GROUP] /ddfm = KR;
  lsmeans [GROUP]* [VISIT];
  repeated [VISIT]/ subject = [SUBJECT] type = UN;
```

run;

- SAS Code for implementing analysis using generalized estimating equation is shown below.

```
proc genmod data = [DATASET];
  class [SUBJECT] [VOLUME] [GROUP];
  model CHG = [GROUP] [VOLUME] [GROUP]* [VOLUME] ;
  lsmeans [GROUP]* [VOLUME];
  repeated subject = [SUBJECT] type = UN or CS;
run;
```

- SAS Code for implementing analysis using MMRM model (cLDA method) is shown below.

\* The coefficient of Estimate must be changed to suit the data.

\*The value of DIF3, DIF5, and DIF10 in the active group is 1 at each time point, otherwise 0.

```
proc mixed data = [DATASET] order = internal;
  class AVISITN(ref = "1") USUBJID;
  model AVAL_ = AVISITN DIF3 DIF5 DIF10/noint s ddfm = kr;
  random USUBJID;
  /* difference between groups in each time point*/
  estimate "Diff (NPC-26 - Placebo) Day3" DIF3 1 /cl;
  estimate "Diff (NPC-26 - Placebo) Day5" DIF5 1 /cl;
  estimate "Diff (NPC-26 - Placebo) Day10" DIF10 1 /cl;
  /* Mean CHG in each time point in each group */
  estimate "LSMean of Change from BL (Placebo) Day3" AVISITN 1 0 0 -1 /cl;
  estimate "LSMean of Change from BL (Placebo) Day5" AVISITN 0 1 0 -1 /cl;
  estimate "LSMean of Change from BL (Placebo) Day10" AVISITN 0 0 1 -1 /cl;
  estimate "LSMean of Change from BL (NPC-26) Day3" AVISITN 1 0 0 -1 DIF3 1 /cl;
  estimate "LSMean of Change from BL (NPC-26) Day5" AVISITN 0 1 0 -1 DIF5 1 /cl;
  estimate "LSMean of Change from BL (NPC-26) Day10" AVISITN 0 0 1 -1 DIF10 1 /cl;
  /*Mean AVAL in each time point in each group */
  estimate "LSMean (Placebo) Day1" AVISITN 0 0 0 1 /cl;
  estimate "LSMean (Placebo) Day3" AVISITN 1 0 0 0 /cl;
  estimate "LSMean (Placebo) Day5" AVISITN 0 1 0 0 /cl;
  estimate "LSMean (Placebo) Day10" AVISITN 0 0 1 0 /cl;
  estimate "LSMean (NPC-26) Day1" AVISITN 0 0 0 1 /cl; *This is same as in common with
Placebo;
  estimate "LSMean (NPC-26) Day3" AVISITN 1 0 0 0 DIF3 1 /cl;
  estimate "LSMean (NPC-26) Day5" AVISITN 0 1 0 0 DIF5 1 /cl;

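### No overall analysis of the primary endpoint adjusts for Day 0 category, although two ranks of improvement mean a different target from Category 3, 4 or 5

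*SAP*

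**What the plan says.** Protocol 7 (rationale) admits a patient whose category "falls into one of Category 3 to 5 on a 7-point ordinal scale", and for the primary endpoint Protocol 5.2.1.1 states: "Assessment on Day 0 will be used as a baseline value". On the scale in SAP Table 2.1 the event is therefore:

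| Day 0 category | Lowest category that counts | Meaning |
|---|---|---|
| 3 | 5 | off oxygen |
| 4 | 6 | off oxygen and off continuous therapy |
| 5 | 7 | discharged |

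SAP 2.1.2.10.1 plans Kaplan-Meier curves by arm, and "the comparison between groups using the log-rank test with a significance level of 5% will be performed as well". No strata are named there or in Protocol 17.2.2. A Cox assessment "with the presence or absence of concomitant antiviral drugs for COVID-19 as a covariate will be performed" follows. The code in SAP 4.7 agrees: `[GROUP]` and `[THERAPY]` are the only terms, and there is no strata statement. Protocol 17.2.2 describes the Cox covariate as the allocation factor, and Protocol 10.2 names standard treatment as that factor.

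Day 0 category is used in three other places:
- SAP 2.1.2.3 lists "category on a 7-point ordinal scale at baseline" among the background variables compared by arm.
- SAP 2.1.2.10.2.10 uses it to select patients for the time to Category 5: "Patients who are in Category 3 or 4 at baseline on a 7-point ordinal scale will be included in the analysis".
- SAP 2.1.2.15 makes it a subgroup factor for the primary endpoint, an addition of version 1.1.

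**The concern.** Three different events are pooled in one curve, and the variable that decides which event applies is in no overall model. It is not an allocation factor either, so nothing balances it between about 40 active and 20 control patients. If one arm happens to start in better-placed categories and category predicts the time to improvement, the log-rank test and the planned Cox model lean the same way. No prespecified overall result would show this.

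The existing uses do not fill the gap. A background table can reveal an imbalance but cannot correct for it. The subgroup runs split about 20 controls up to three ways and give no pooled estimate. The fixed-target analyses (discharge; Category 6 or 7; Category 5 from baseline 3 or 4) avoid the moving target but are unadjusted too. The SAP does put the baseline value into its repeated-measures models for blood gases, CT findings and cytokines, so the idea is already part of the plan.

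Precision and protection against chance are at stake, not the validity of the primary test.

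**Working it through.** **1. The plan's own figure.** Protocol 18 gives 82.1% power for 40 v 20 patients, normal times with means 10 and 14, SD 4.5, log-rank test, two-sided 5%. With Z = Σ(d₁ − d·n₁/n) / √Σ[d(n₁/n)(1 − n₁/n)(n − d)/(n − 1)], censoring at Day 28 and 5,000 runs, power is 82.3% with continuous times and 83.1% with whole days. The figure reproduces. It contains no component for baseline category.

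**2. Assumptions.** The documents give neither the category mix nor the effect of category. Two mixes are assumed for Categories 3/4/5: 20/65/15 and 10/85/5. The gap is the shift between adjacent categories (0, 2 or 4 days, Category 3 slowest). In the normal model the total SD stays at 4.5. Scoring the categories +1, 0, −1:
- 20/65/15: variance 0.35 − 0.05² = 0.3475. A 2-day gap explains 4 × 0.3475 = 1.39 of 20.25 (7%), and a 4-day gap 16 × 0.3475 = 5.56 (27%). Within-category SD is √18.86 = 4.34 and √14.69 = 3.83.
- 10/85/5: variance 0.15 − 0.05² = 0.1475. The shares are 0.59 (3%) and 2.36 (12%); within-category SD is 4.43 and 4.23.

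The alternative model is Weibull: shape 2.35, control median 14, hazard ratio (HR) 2.2 within category. Randomisation is 2:1 in blocks of 3 within a 70:30 non-prognostic stratum. Times are whole days, and non-improvers stay at risk to Day 28.

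**3. Change in Cox power** (percentage points) when category joins group and therapy; 5,000 runs per cell, Breslow ties, Wald test. Each cell shows mix 20/65/15, then 10/85/5.

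| Model | No gap | 2-day gap | 4-day gap |
|---|---|---|---|
| Normal, all improve | +0.6, -0.3 | +2.6, +1.4 | +11.6, +5.3 |
| Weibull, all improve | -0.7, -1.0 | +1.7, +0.6 | +7.2, +3.4 |
| Normal, 5% never improve | +1.8, +0.7 | +3.8, +0.5 | +11.6, +5.8 |
| Weibull, 5% never improve | +1.3, 0.0 | +2.5, +1.3 | +5.6, +2.5 |

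SAP 4.7 names no tie method. With Efron ties (all improving) the ranges are -0.5 to +0.4, -0.2 to +2.9 and +3.1 to +9.8. With a different order of the categories (20/65/15), gains are +1.0 to +2.9 at 2 days and +5.6 to +11.7 at 4 days.

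**4. Type I error.** Planned Cox 3.6-4.8%; Cox with category 4.2-5.8%; log-rank, unstratified or stratified by category, 4.9-5.9%.

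**5. Stratified minus unstratified log-rank power.** No gap: -4.8 to +1.2 points. 2 days: -1.9 to +4.7. 4 days: +0.6 to +15.1.

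**6. Chance imbalance.** The SD of the difference in mean category between arms is √[variance × (1/40 + 1/20)]. At 20/65/15 this is √(0.3475 × 0.075) = 0.161, so a difference of 0.2 or more lies beyond 1.24 SD and occurs in about 21% of trials. At 10/85/5 the SD is 0.105 and the rate about 6%. Simulation gives 21-22% and 5.5-6.0%. These rates count both directions.

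The next table covers trials with no drug effect (20,000 simulated per scenario, mix 20/65/15), restricted to the roughly 2,100 in which imbalance favours active by 0.2 or more. It shows false positives for active (nominal 2.5%) and the median HR; values above 1 favour active. Each cell is normal / Weibull.

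| | 2-day gap | 4-day gap |
|---|---|---|
| Planned log-rank | 4.4 / 5.0% | 9.8 / 6.3% |
| Planned Cox | 3.0 / 4.0%, HR 1.10 / 1.10 | 7.1 / 4.9%, HR 1.23 / 1.16 |
| Cox with category | 1.7 / 1.9%, HR 0.99 / 1.01 | 2.4 / 1.9%, HR 0.99 / 0.99 |

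The standard error of these rates is 0.3-0.7 points. With no gap, the planned log-rank rate in such trials is 2.8 / 2.5%.

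**The case against.** The strongest case against is that this is a preference, not an error. The log-rank test is valid, protocol and SAP agree on it, and the Cox model carries the covariate that the protocol names. The adjusted model would be supportive only, so the false-positive rates of the primary test would not change. All of this is true.

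Four further points limit the size:
- **Conditional rates.** Imbalance towards active arises in about 2,100 / 20,000 = 10.5% of trials. The overall excess is therefore 0.105 × (4.4 to 5.0 − 2.5) = 0.2 to 0.3 points at a 2-day gap, and 0.105 × (6.3 to 9.8 − 2.5) = 0.4 to 0.8 points at 4 days.
- **Unequal test sizes.** The planned Cox test runs slightly below 5%, so part of the gain comes from test size. Subtracting each no-gap result from its own row leaves -0.2 to +2.4 points at 2 days and +2.5 to +11.0 at 4 days.
- **The gap may be small.** A patient in Category 3 is sicker but has the nearer target; one in Category 5 is better but must be discharged. These can offset each other. Entry requires room-air SpO₂ of 93% or less, so Category 5 may be rare and a concentrated mix is plausible.
- **Sparse cells.** At 10/85/5, Category 5 holds about 0.05 × 60 = 3 patients, and merging it with Category 4 pools different targets again.

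These points set the weight; they do not remove the gap. The background comparison would show an imbalance, but no planned overall estimate would take it into account.

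**Conclusion.** The concern holds as an optional improvement. The omission is certain from the text and the code; its consequence is conditional. A 4-day gap is a strong assumption, since it equals the whole assumed treatment effect. The 2-day case is the more cautious one, and there the power gain is small. If category is not prognostic there is no real gain, and the loss is at most about 1.0 point of Cox power in the Breslow runs. The main value is protection: when imbalance favours active and category matters, the planned Cox model shows an apparent benefit (median HR 1.10 to 1.23 with no drug effect), and the adjusted model brings it back to about 1.

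**What to change.** Make and date these changes before unblinding:

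1. In SAP 2.1.2.10.1, add Day 0 category (class variable, 3/4/5) to the Cox model beside the allocation factor as recorded at randomisation. State in one sentence that antiviral use yes/no is that factor, if it is. This is the natural reading, because SAP 2.1.2.15 drops antiviral use from its Cox subgroup runs, but no sentence says so.
2. In SAP 4.7, add `[BASECAT]` after `[THERAPY]` in both the class and the model statements.
3. Fix, on blinded counts, the cell size below which a category is merged with its neighbour.
4. Report the protocol's Cox model and the adjusted one side by side, clearly labelled. The two hazard ratios are different quantities (for example, medians of 2.15 and 2.61 at a 4-day normal gap).
5. Keep the unstratified log-rank test as primary. Add a log-rank test stratified by Day 0 category as a sensitivity analysis only, since it can lose up to 4.8 points of power. Add the allocation stratum only where blinded counts allow.

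The cost is a few sentences, one variable already recorded on Day 0, one extra analysis and the dated note of reason and effect that Protocol 17.6 requires. The primary test and its power statement do not change. SAP version 1.1 is dated December 2021, after the planned study period ended in October 2021, so the change is credible only if its date precedes unblinding.
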